3.3.4 Removal of patients from therapy or assessments

3.3.4.1 Removal of individual patients

An individual patient is to be withdrawn from trial participation if the patient withdraws consent for trial participation, without the need to justify the decision.

An individual patient is to be withdrawn from all trial drugs (nintedanib and sildenafil/matching placebo) if:

- The patient withdraws consent for study treatment, without the need to justify the decision;
- The patient needs to take concomitant drugs that interfere with the investigational products ([section 4.2.2](#));
- The patient can no longer be treated with trial medication for other medical reasons (such as surgery, adverse events, other diseases, or pregnancy);

If a patient becomes pregnant or pregnancy is suspected during the trial, the patient will be permanently discontinued from study treatment and will be followed up until birth or otherwise termination of pregnancy, please see [section 5.3.7](#).

- The patient experiences signs or symptoms of acute myocardial ischemia or stroke;
- The patient experiences signs of hepatic injury, defined as one of the following:
 - ALT and/or AST \geq 8 fold ULN
 - ALT and/or AST \geq 3 fold ULN and total bilirubin \geq 2 fold ULN
 - ALT and/or AST \geq 3 fold ULN and unexplained INR $>$ 1.5
 - ALT and/or AST \geq 3 fold ULN and unexplained eosinophilia ($>$ 5%)
 - ALT and/or AST \geq 3 fold ULN and appearance of fatigue, nausea, vomiting, right upper abdominal quadrant pain or tenderness, fever and/or rash.

For potential drug induced liver injury (DILI) follow up requirements please see [sections 4.2.1.3](#) and [5.3.6.1](#).

Treatment with nintedanib must be permanently discontinued in the following situations:

- In the opinion of the investigator, the patient experiences unacceptable toxicity due to nintedanib despite dose adjustments and supportive care;
- Gastrointestinal perforation;
- Major surgery including abdominal or intestinal surgery;
- Signs or symptoms of deep vein thrombosis or pulmonary embolism;
- Treatment interruption longer than 4 weeks (continuous).

In addition, permanent discontinuation of nintedanib should be considered in the following situations:

- Patient who requires full dose therapeutic anticoagulation or high dose antiplatelet therapy;
- Increased risk of bleeding (e.g., gross/ frank haemoptysis or haematuria, active gastrointestinal bleeding or ulcers).

In such cases, continuation of nintedanib should be discussed with the patient and the decision based on an individual benefit-risk assessment documented in the source data.

Treatment with sildenafil/matching placebo must be permanently discontinued in the following situations:

- In the opinion of the investigator, the patient experiences unacceptable toxicity due to sildenafil despite supportive care;
- Hypotension (SBP < 100 mmHg or DBP < 50 mmHg) accompanied by symptoms;
- In the event of any sudden visual defect;
- Prolonged erections and priapism;
- Treatment interruption longer than 4 weeks (continuous).

If a patient discontinues all study drugs (nintedanib and sildenafil/matching placebo), he/she will undergo the procedures for early treatment discontinuation and will be invited to attend all planned study visits until week 24 as outlined in the [flow chart](#).

For all patients the reason for withdrawal (e.g. adverse events) must be recorded in the electronic case report form (eCRF). These data will be included in the trial database and reported.

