4.2.2 Restrictions

4.2.2.1 Restrictions regarding concomitant treatment

Concomitant medications (or therapy) to provide adequate care may be given as clinically necessary. If restricted concomitant therapy is necessary, treatment with study medication should be permanently discontinued (except in case of acute IPF exacerbations – refer to [section 4.2.1.1](#)).

Table 4.2.2.1:1 Permitted and Restricted Concomitant therapy

	Prior to randomisation	During treatment period	After Visit 7 (Follow-up Period)	After early EOT⁹
Nintedanib	Permitted (150 mg bid dose only)	Study medication	Permitted	Not permitted
Sildenafil	Not permitted in the 4 weeks prior to visit 2 ¹	Study medication	Permitted	Not permitted
Pirfenidone, N-acetylcysteine, Azathioprine, Cyclophosphamide, Cyclosporine	Not permitted in the 4 weeks prior to visit 2 ¹	Not permitted	Not permitted	Permitted
Prednisone and other oral corticosteroid ²	Not permitted in the 4 weeks prior to visit 2 ¹	Not permitted	Not permitted	Permitted

Table 4.2.2.1:1 (continued) Permitted and Restricted Concomitant therapy

Investigational Medication	Not permitted in the 4 weeks prior to visit 2 ¹	Not permitted	Not permitted ¹⁰	Not permitted
Nitrates	Not permitted in the 4 weeks prior to visit 2 ¹	Not permitted	Not permitted	Permitted
Prostaglandins ³ , endothelin-1 antagonists ⁴ or phosphodiesterase inhibitors ⁵ or a stimulator of guanylatcyclase ⁶	Not permitted in the 4 weeks prior to visit 2 ¹	Not permitted	Not permitted	Not permitted
Potent CYP3A4 inhibitors such as ketoconazole, itraconazole and ritonavir	Not permitted in the 4 weeks prior to visit 2 ¹	Not permitted	Not permitted	Permitted
L-arginine, grapefruit juice or St John's wort	Not permitted in the 4 weeks prior to visit 2 ¹	Not permitted	Not permitted	Permitted
Anticoagulation at full dose ⁷ , antiplatelet therapy at high dose ⁸ , fibrinolysis	Permitted	Not permitted	Not permitted	Permitted

1. Washout should not occur until after patient has signed informed consent
2. Prednisone >15 mg daily or >30 mg every 2 days OR equivalent dose of other oral corticosteroids.
3. e.g., epoprostenol, treprostini
4. e.g., bosentan, sitaxsentan, ambrisentan
5. e.g., sildenafil, tadalafil, vardenafil
6. e.g., riociguat

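### Sections 3.3.4.1 and 4.2.2.1 of the protocol conflict on stopping study drug when a patient comes to need full-dose anticoagulation or high-dose antiplatelet therapy

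*Protocol*

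**What the plan says.** **Protocol 4.2.2.1.** The text above the table reads: "If restricted concomitant therapy is necessary, treatment with study medication should be permanently discontinued", with one carve-out, "except in case of acute IPF exacerbations". The last row of Table 4.2.2.1:1 covers full-dose anticoagulation, "antiplatelet therapy at high dose" and fibrinolysis. It shows them as not permitted during the treatment period and permitted after early EOT. Footnotes 7 and 8 exempt only prophylactic use and heparin flush. Footnote 9 reserves the early-EOT column for patients who have come off all study medication and keep attending visits.

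**Protocol 3.3.4.1, first list.** "An individual patient is to be withdrawn from all trial drugs" in several situations. One of them is: "The patient needs to take concomitant drugs that interfere with the investigational products". This item refers the reader to section 4.2.2.

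**Protocol 3.3.4.1, later list.** Here "permanent discontinuation of nintedanib should be considered in the following situations", the first being: "Patient who requires full dose therapeutic anticoagulation or high dose antiplatelet therapy". The text then adds that "continuation of nintedanib should be discussed with the patient and the decision based on an individual benefit-risk assessment", recorded in the source data. Sildenafil/placebo is not mentioned for this case.

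**The concern.** Both texts address the same patient and the same two classes of therapy. One directs that study medication be stopped for good. The other makes stopping a matter for consideration, and for nintedanib only. An investigator who continues nintedanib after the assessment described in section 3.3.4.1 departs from section 4.2.2.1. One who stops automatically under section 4.2.2.1 bypasses that individual assessment.

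This matters first for conduct. Section 2.3 lists bleeding among the nintedanib risks and gives those risks as the reason for excluding such patients at entry. Handling of the same need when it arises on treatment should not depend on which section a site reads.

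Three reporting items also depend on the reading:

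- whether the early EOT visit is triggered, since flow chart footnote 17 ties it to stopping all study drugs;
- the date of last trial drug intake, and with it the on-treatment window for the SAE endpoint (SAP 6.1: 28 days after last intake);
- whether medical review records an important violation under SAP Table 6.2: 1, category C6 (drug not stopped although the section 3.3.4.1 criteria were met) or D1 (prohibited therapy while on any trial drug).

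**Working it through.** The plan gives no figure to reproduce. The check is a comparison of texts, followed by one line of arithmetic for scale.

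**Step 1. The two rules side by side**

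| | Section 4.2.2.1 and its table | Section 3.3.4.1, later list |
|---|---|---|
| Therapies | Full-dose anticoagulation, high-dose antiplatelet therapy, fibrinolysis | Full-dose anticoagulation, high-dose antiplatelet therapy |
| Strength | Should be permanently discontinued | Should be considered |
| Drugs covered | Study medication | Nintedanib |
| Exception or discretion | Acute IPF exacerbation only | Individual documented benefit-risk decision |

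The rules differ in strength and in the drugs covered. Fibrinolysis appears only on the left, so the conflict is limited to the other two classes.

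**Step 2. Does the first list of section 3.3.4.1 settle it?** It requires withdrawal from both drugs when an interfering concomitant drug is needed, and it points to section 4.2.2. It can be read to include these therapies, but the documents link them to bleeding risk rather than to interference. The conflict in Step 1 does not need this reading, because the table names the therapies directly.

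**Step 3. Table status of each possible action, outside acute IPF exacerbation**

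| Action | Column of Table 4.2.2.1:1 | Therapy |
|---|---|---|
| Stop all study drugs | After early EOT (footnote 9) | Permitted |
| Stop nintedanib only | Treatment period, since sildenafil/placebo continues | Not permitted |
| Continue both | Treatment period | Not permitted |

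Two of the three actions fall in a not-permitted cell, yet the later list of section 3.3.4.1 leaves both open. The middle row is an inference: footnote 9 opens the other column only to patients off all study medication, and no footnote defines the treatment-period column for a patient on one drug.

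**Step 4. Consequence in the SAP.** D1 applies during treatment with any trial drug. A patient kept on nintedanib in line with section 3.3.4.1, or kept on sildenafil/placebo alone, could therefore be recorded under D1. C6 relies on section 3.3.4.1, whose lists differ in strength. Both categories go to medical review, and neither excludes a patient from an analysis set.

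**Step 5. Scale.** With 125 patients planned per arm (synopsis), reclassifying one patient's SAE as on-treatment or not changes that arm's percentage by

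100 × 1/125 = 0.8 percentage points.

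This assumes that all 125 are treated. With 100 treated, as an illustration, it is 100 × 1/100 = 1.0. The SAE comparison is exploratory (protocol 7.1). The primary analysis keeps observations made after premature discontinuation (SAP 7.4.1), so the stopping rule does not change which SGRQ data enter it.

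**The case against.** The strongest reply is that the specific text governs the general one. Section 4.2.2.1 states a general rule for all restricted drugs and uses should, not must. The later list in section 3.3.4.1 singles out these two therapies and sets a process. That reading is possible, but the protocol does not state it. The table also has its own row for these therapies, so both texts are specific, and the not-permitted entry is not softened.

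A second reply is that the conflict runs one way: a site that holds the benefit-risk discussion and then stops all study drugs satisfies both texts. That is correct. But if only that outcome complies, the discretion in section 3.3.4.1 has no content; if the discretion is real, using it to continue departs from section 4.2.2.1.

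A third reply is that few patients are left. Acute myocardial ischemia or stroke already stops all drugs, deep vein thrombosis or pulmonary embolism already stops nintedanib, prophylactic doses are exempt, and patients needing these therapies are excluded at entry. This narrows the group without emptying it. After deep vein thrombosis or pulmonary embolism, the question of sildenafil/placebo remains.

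The statistical consequences are indeed small. An SAE is reclassified only if it falls between two candidate on-treatment windows, and nothing in the documents suggests that the arms would be affected differently. The two-of-three count describes the table and does not measure an effect on results. Temporary interruption, which section 4.2.1.1 allows in some circumstances, is outside that count.

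**Conclusion.** The concern holds. For the same two therapies, the current protocol text gives a direction to stop study medication in one place and a discretionary, nintedanib-only decision in another, with no order of precedence. The finding rests on the wording of section 4.2.2.1 with its table and of the later list in section 3.3.4.1. It does not depend on whether the first list's reference to interference covers these drugs.

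The weight lies in consistent handling of a named bleeding risk and in coherent violation coding. The effect on results is minor: none on the primary analysis, and at most 0.8 percentage points per reclassified patient in one arm's SAE percentage, assuming 125 treated. The number of such patients cannot be derived from the documents. This should be corrected, but it does not threaten the trial's main conclusion.

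**What to change.** Reconcile section 3.3.4.1 (both lists and the paragraph on individual assessment) with section 4.2.2.1, Table 4.2.2.1:1 and footnote 9. The result should be one rule for full-dose anticoagulation and high-dose antiplatelet therapy arising on treatment. It should state whether it applies to nintedanib, sildenafil/placebo or both, and which table column applies to a patient who remains on only one of them. The clinical content is for the sponsor's medical team to decide; this review takes no position on it.

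Then check that SAP categories C6 and D1 follow the reconciled rule, so that a site complying with it is not recorded as a violation.

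The cost is amendment wording, a clarification to sites and a check of two rows in SAP Table 6.2: 1. No procedures or data collection are added.

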3.3.4.2 Discontinuation of the trial by the sponsor

Boehringer Ingelheim reserves the right to discontinue the trial overall or at a particular trial site at any time for the following reasons:

1. Failure to meet expected enrolment goals overall or at a particular trial site
2. Emergence of any efficacy/safety information invalidating the earlier positive benefit-risk-assessment that could significantly affect the continuation of the trial
3. Violation of good clinical practice (GCP), the clinical trial protocol (CTP), or the contract disturbing the appropriate conduct of the trial

The Investigator / the trial site will be reimbursed for reasonable expenses incurred in case of trial termination (except in case of the third reason).

4. TREATMENTS

4.1 TREATMENTS TO BE ADMINISTERED

4.1.1 Identity of BI investigational product and comparator product

Table 4.1.1:1 Nintedanib

Substance:	Nintedanib (Ofev [®])
Pharmaceutical formulation:	Soft gelatine capsule
Source:	BI Pharma GmbH & Co.KG
Unit strength:	150 mg, 100 mg
Posology	1 capsule, bid
Route of administration:	Oral (swallowed)

Table 4.1.1:2 Sildenafil and placebo matching sildenafil

Substance:	Sildenafil	Placebo
Pharmaceutical formulation:	Capsules	Capsules
Source:	BI Pharma GmbH & Co.KG tablets for overencapsulation sourced from Pfizer	BI Pharma GmbH & Co.KG
Unit strength:	20 mg	Not applicable
Posology	1 capsule, tid	1 capsule, tid
Route of administration:	Oral (swallowed)	Oral (swallowed)

4.1.2 Method of assigning patients to treatment groups

Patient randomization to treatment groups will be determined by an IRT system. Access to the randomization code will be controlled and documented. All necessary instructions for

using the IRT system will be described in a user guide/manual, a copy of which will be available in the ISF.

At visit 2, eligible patients will be randomised via IRT to one of the two treatment groups. Patients will have an equal chance of being randomised to nintedanib co-administered with sildenafil or to nintedanib co-administered with placebo matching sildenafil.

4.1.3 Selection of doses in the trial

Nintedanib: A dose of 150 mg bid (total daily dose of 300 mg) was selected for this trial as this is the recommended dose based on prescribing information in participating countries. Dose adjustments are permitted as per section 4.1.4.1 and [section 4.2.1](#).

Sildenafil: A dose of 20 mg tid (total daily dose of 60 mg) was selected for this trial as this is the recommended dose for the approved indication of PAH based on the prescribing information in participating countries. This was also the dose studied in IPF patients in the STEP-IPF study [[R12-3686](#)]. No dose adjustment is allowed during this study.

4.1.4 Drug assignment and administration of doses for each patient

Drug is dispensed by the investigator, study coordinator or pharmacist, depending on the site structure. IRT will be used to assign appropriate treatment kits to each patient.

To ensure patients receive adequate supply of study medication, kits will be dispensed at clinic visits in quantities outlined in table 4.1.4:1

Table 4.1.4:1 Quantity of medication kits dispensed:

Visit	Nintedanib Kit	Sildenafil / Matching Placebo Kit
2	1	1
3	1	1
4	1	1
5	3	3

4.1.4.1 Nintedanib

- Treatment with nintedanib will consist of 1 capsule twice daily (bid).
- The first administration of nintedanib will be taken in the clinic at visit 2.
- The patients should swallow nintedanib unchewed with a glass of water (250mL) and should observe a dosing interval of 12 hours.
- Nintedanib should be taken at the same time every day between 06:00 and 11:00 in the morning and between 18:00 and 23:00 in the evening.

- Because nintedanib may cause stomach discomfort, it is recommended to be taken at the end of a meal.
- If a dose of nintedanib is missed, administration should resume at the next scheduled time at the recommended dose. Double doses should not be taken to make up for forgotten capsules.

Dose adjustment of nintedanib is allowed to manage adverse events: 300 mg daily (150 mg bid) may be reduced to 200 mg daily (100 mg bid). For additional details please refer to [section 4.2.1](#).

Dose reductions or re-escalation of nintedanib must be done in the clinic at a dose adjustment visit (refer to the [flow chart](#)), as a new medication kit will need to be assigned through IRT. The amount of study drug dispensed at the time of dose reduction and dose re-escalation is dependent upon the amount of time between the dose adjustment visit and the next planned study visit. IRT will assign only the number of study medication kits needed until the next planned patient visit.

4.1.4.2 Sildenafil and matching placebo

- Treatment with sildenafil (or matching placebo) will consist of 1 capsule three times daily (tid).
- The first administration of sildenafil (or matching placebo) will be taken in the clinic at visit 2.
- Sildenafil capsules should be taken approximately 6 to 8 hours apart.
- It is recommended that nintedanib and sildenafil are administered together at the same time in the morning and evening at the end of a meal, with the third sildenafil dose administered at the midpoint.
- If a dose of sildenafil is missed, administration should resume at the next scheduled time at the recommended dose. Double doses should not be taken to make up for forgotten capsules.
- No dose adjustments are allowed for sildenafil within this study.

4.1.5 Blinding and procedures for unblinding

4.1.5.1 Blinding

Patients, investigators and everyone involved in trial conduct or analysis or with any other interest in this double-blind trial (apart from the DMC) will remain blinded with regard to the randomized treatment assignments until after database lock.

The randomization code will be kept secret by Clinical Trial Support up to database lock.

The DMC may review unblinded data upon request, and only under conditions that ensure that patients, investigators and everyone involved in trial conduct or analysis or with any other interest in this double-blind trial will remain blinded.

4.1.5.2 Unblinding and breaking the code

Emergency unblinding will be available to the Investigator / Pharmacist / investigational drug storage manager via IRT. It must only be used in an emergency situation when the identity of the trial drug must be known to the Investigator in order to provide appropriate medical treatment or otherwise assure safety of trial participants. The reason for unblinding must be documented in the source documents and/or appropriate CRF page along with the date and the initials of the person who broke the code.

Due to the requirements to report Suspected Unexpected Serious Adverse Reactions (SUSARs), it may be necessary for a representative from Boehringer Ingelheim's Pharmacovigilance group to access the randomisation code for individual patients during trial conduct. The access to the code will only be given to authorised Pharmacovigilance representatives and not be shared further.

For Japan only: In this blinded trial, an emergency code break will be available to the Investigator / the sub-Investigators via the IRT system. This code break may only be accessed in emergency situations when the identity of the trial drug must be known to the Investigator /the sub-Investigators in order to provide appropriate medical treatment or if required to assure the safety of trial participants. Each site receives a manual from the IRT provider that contains instructions on how to unblind the treatment of a patient via the IRT (via 24-hour Emergency helpline). If the code break for a patient is accessed, the sponsor must be informed immediately. The reason for accessing the code break, together with the date, must be documented on the appropriate eCRF page. In case third party needs to break the code, however, when the Investigator cannot be reached, the code can be opened by calling emergency code manager.

4.1.6 Packaging, labelling, and re-supply

Nintedanib will be packaged in blisters (containing either nintedanib 100 mg or nintedanib 150 mg). Each blister will contain 10 capsules. Seven blisters will be packaged into one child-resistant tamper-evident wallet (i.e. 70 capsules/wallet).

Sildenafil / matching placebo will be packaged in blisters. Each blister will contain 15 capsules. Seven blisters will be packaged into one child-resistant tamper-evident wallet (i.e. 105 capsules/wallet).

For details of packaging and the description of the label, refer to the ISF.

Re-supplies of study medication are planned due to the long duration of the study. The medication for re-supply will be packaged in an identical manner as the medication for initial supply.

4.1.7 Storage conditions

Drug supplies will be kept in their original packaging and in a secure limited access storage area according to the recommended storage conditions on the medication label. A temperature log must be maintained for documentation.

If the storage conditions are found to be outside the specified range, the local clinical monitor (as provided in the list of contacts) must be contacted immediately.

4.1.8 Drug accountability

The Investigator and/or Pharmacist and/or investigational drug storage manager will receive the investigational drugs delivered by the sponsor when the following requirements are fulfilled:

- Approval of the trial protocol by the IRB / ethics committee,
- Availability of a signed and dated clinical trial contract between the sponsor and the head of the investigational site,
- Approval/notification of the regulatory authority, e.g. competent authority,
- Availability of the curriculum vitae of the principal Investigator,
- Availability of a signed and dated clinical trial protocol
- If applicable, availability of the proof of a medical license for the principal Investigator
- In the USA, availability of Form 1572

The Investigator and/or Pharmacist and/or investigational drug storage manager must maintain records of the product's delivery to the trial site, the inventory at the site, the use by each patient, and the return to the sponsor or alternative disposal of unused products.

These records will include dates, quantities, batch / serial numbers, expiry ('use- by') dates, and the unique code numbers assigned to the investigational product and trial patients. The Investigator / Pharmacist / investigational drug storage manager will maintain records that document adequately that the patients were provided the doses specified by the CTP and reconcile all investigational products received from the sponsor. At the time of return to the sponsor or appointed CRO, the Investigator / Pharmacist / investigational drug storage manager must verify that all unused or partially used drug supplies have been returned by the clinical trial patient and that no remaining supplies are in the Investigator's possession.

